5.2.4. Linear Regression PK Parameters versus Hepatic Function

Linear regression will be used to analyze the potential relationship between appropriate PK parameters (eg, AUC_{inf} , AUC_{last} , C_{max} , f_u , $AUC_{inf,u}$, $AUC_{last,u}$, $C_{max,u}$) and hepatic function as a continuous explanatory variable (using either continuous serum albumin, prothrombin time or total bilirubin, each modelled separately). Estimates of the slope and intercept, together

[figure not shown]
Pfizer Confidential

with a 90% CI, and the coefficient of determination (i.e. R-squared and adj-R-squared) may be obtained from the model. Example SAS code is given in Appendix 1.

Residuals from the models will be examined for normality and the presence of outliers via visual inspection of plots of residuals vs predicted values and normal probability plots of residuals but these will not be included in the clinical study report. If there are major deviations from normality or outliers (where studentized residuals are greater than 3 or less than - 3) then the effect of these on the conclusions may be investigated through alternative transformations and/or analyses excluding outliers. Alternative model structure may also be considered. Justification for any alternative to the planned analysis will be given in the report of the study if applicable.

CCI

CCI

5.3. Methods to Manage Missing Data

For the analysis of safety endpoints, the sponsor data standard rules for imputation will be applied.

5.3.1. Pharmacokinetic Concentrations Below the Limit of Quantification

In all data presentations (except listings), concentrations below the limit of quantification (BLQ) will be set to zero. In listings BLQ values will be reported as “<LLQ”, where LLQ will be replaced with the value for the lower limit of quantification.

5.3.2. Pharmacokinetic Deviations, Missing Concentrations and Anomalous Values

In summary tables and plots of median/mean profiles, statistics will be calculated having set concentrations to missing if 1 of the following cases is true:

1. A concentration has been collected as ND (ie, not done) or NS (ie, no sample),
2. A deviation in sampling time is of sufficient concern or a concentration has been flagged anomalous by the pharmacokineticist/clinical team.

Note that summary statistics will not be presented at a particular time point if more than 50% of the data are missing.

5.3.3. Pharmacokinetic Parameters

Actual PK sampling times will be used in the derivation of PK parameters.

If a PK parameter cannot be derived from a participant's concentration data, the parameter will be coded as NC (ie, not calculated). Note that NC values will not be generated beyond the day that a participant discontinues.

In analysis and summary tables, statistics will be calculated by setting NC values to missing; and statistics will be presented for a particular group with ≥ 3 evaluable measurements.

If an individual participant has a known biased estimate of a PK parameter (due for example to an unexpected event such as vomiting before all the compound is adequately absorbed in the body), this will be footnoted in summary tables/figures and will not be included in the calculation of summary statistics or statistical analyses.

6. ANALYSES AND SUMMARIES

Data collected before baseline will only be listed, unless otherwise stated.

Unless otherwise stated, all analyses, summaries and listings will be produced by group (as outlined in Section 5) which would include all 4 groups in the same analysis/output.

6.1. Primary Endpoint(s)

6.1.1. PF-07081532 PK Parameters

- Estimand strategy: Not applicable
- Analysis set: PF-07081532 Concentration and Pharmacokinetic Parameter Set

6.1.1.1. Main Analysis

C_{max} , AUC_{inf} (if data permit), AUC_{last} , fu , $AUC_{inf,u}$, $AUC_{last,u}$ and $C_{max,u}$ will be listed, summarized descriptively and analyzed by group for participants in the PK parameter set (as defined in Section 4). Missing values will be handled as detailed in Section 5.3.

A one-way analysis of variance (ANOVA) described in Section 5.2.3, that includes all 4 groups in the same model, will be used to compare the natural log transformed of C_{max} , AUC_{inf} , AUC_{last} , fu , $AUC_{inf,u}$, $AUC_{last,u}$, and $C_{max,u}$ of PF-07081532 separately, for each of the hepatic impairment groups (Test, Groups 2, 3, 4) to the healthy normal hepatic function group (Reference, Group 1).

For summary statistics and median or mean plots by sampling time, the nominal PK sampling time will be used. For individual participant plots by time, the actual PK sampling time will be used. The plasma PK parameters of PF-07081532 for each group will be summarized as specified in Table 7 below.

Table 7. Summary statistics to be produced for Plasma PK Parameters of PF-07081532

Parameter	Summary Statistics
C_{max} , AUC_{inf}^* , AUC_{last} , fu , $AUC_{inf,u}^*$, $AUC_{last,u}$, and $C_{max,u}$	N, arithmetic mean, median, cv%, standard deviation, minimum, maximum, geometric mean and geometric cv%.

* if data permits

The following plots will be presented:

- *Box and whisker plots for individual PK parameters (AUC_{inf} , AUC_{last} , C_{max} , fu , $AUC_{inf,u}$, $AUC_{last,u}$ and $C_{max,u}$) will be constructed by group and overlaid with geometric means.*

6.1.1.2. Sensitivity/Supplementary Analyses

CCI

Plots of PK parameters (eg, AUC_{inf} , AUC_{last} , C_{max} , fu , $AUC_{inf,u}$, $AUC_{last,u}$ and $C_{max,u}$) versus hepatic function at baseline (e.g. serum albumin, prothrombin time or total bilirubin, plotted separately) will be constructed, with a regression line and 90% confidence region included from the main linear regression model.

6.2. Secondary Endpoint(s)

Any clinical laboratory, ECG, BP, and pulse rate abnormalities of potential clinical concern will be described.

No formal analyses are planned for safety data.

The safety endpoints detailed in Section 3.2 will be listed and summarized in accordance with sponsor reporting standards based on the safety population (as defined in Section 4), with more details provided below.

6.2.1. Adverse Events

Adverse events will be summarised by group and overall, in accordance with sponsor reporting standards using the safety population defined in Section 4.

If applicable, subject discontinuations due to adverse events will be detailed and summarized.

6.2.2. Laboratory Data

Laboratory data will be listed and summarized by group and overall, in accordance with the sponsor reporting standards using the safety population defined in Section 4. Baseline is as defined in Section 3.2.

6.2.3. Vital Signs

Absolute values and changes from baseline in seated systolic and diastolic blood pressure and pulse rate will be summarised by group, according to sponsor reporting standards using the safety population defined in Section 4. Baseline is as defined in Section 3.2.

Maximum and minimum absolute values and maximum changes from baseline for seated vital signs will also be summarised descriptively by group using categories as defined in Appendix 2. Numbers and percentages of participants meeting the categorical criteria will be provided. All planned and unplanned post dose time points will be counted in these categorical summaries. All values meeting the criteria of potential clinical concern will be listed.

6.2.4. ECG

Absolute values and changes from baseline in QT interval, heart rate, QTcF interval, PR interval and QRS interval will be summarised by group using sponsor reporting standards and the safety population defined in Section 4. Tables will be paged by parameter. Baseline is as defined in Section 3.2.

Maximum absolute values and changes from baseline for QTcF, PR and QRS will also be summarised descriptively by group using categories as defined in Appendix 2. Numbers and percentages of participants meeting the categorical criteria will be provided. All planned and unplanned post dose time points will be counted in these categorical summaries. All values meeting the criteria of potential clinical concern will be listed.

CCI

CCI

[REDACTED]

[REDACTED]

[REDACTED]

[REDACTED]	[REDACTED]	[REDACTED]

[REDACTED]

[REDACTED]

[REDACTED]

[REDACTED]

[REDACTED]

[REDACTED]

[REDACTED]

CCI

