### 2.3.1. Risk Assessment

Potential Risk of Clinical Significance	Summary of Data/Rationale for Risk	Mitigation Strategy
Study Intervention PF-07081532		
Gastrointestinal adverse reactions	
The potential risks are based on product labeling for injectable GLP-1R agonists (ie, liraglutide, exenatide, semaglutide and dulaglutide).
 
In addition, gastrointestinal adverse events, the majority of which were mild in severity, have been observed in the clinical program with PF-07081532.
	
The single dose and dose level administered in this study minimize any potential risk.
 
Participants are monitored during the clinical studies to prevent potential sequelae of any severe gastrointestinal reactions, eg, dehydration.

Hypoglycemia	
Clinical trials with injectable GLP-1R agonists have not demonstrated an increased risk for hypoglycemia. However, when administered in combination with anti-diabetic agents that are known to have an increased risk of hypoglycemia (such as insulin or sulfonylureas), an increased risk for hypoglycemia was observed.
	
The single dose and dose level administered in this study minimize any potential risk.
 
Study includes inpatient monitoring of the participants following administration of a single dose of the investigational product.

Increased heart rate	
Based on the product labeling for the injectable GLP-1R agonist liraglutide for obesity, mean increases in resting heart rate ranged 2 to 3 bpm in clinical trials, with some participants experiencing greater increases in resting heart rate, up to 10-20 bpm.
 
Following single dose administration of PF-07081532 in the completed FIH study, variable increases in heart rate were observed; the majority of individual values remained within normal ranges, and, throughout the study, no AEs or clinical symptoms related to vital sign parameters were reported.
	
The single dose and dose level administered in this study minimize any potential risk.
 
Study includes inpatient monitoring of the participants following administration of a single dose of the investigational product.

PFIZER CONFIDENTIAL

Potential Risk of Clinical Significance	Summary of Data/Rationale for Risk	Mitigation Strategy

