**5.2.2. Additional Exclusion Criteria for Group 1 *Only* (without Hepatic Impairment)**

1. Evidence of chronic liver disease including history of hepatitis, hepatitis B, or hepatitis C or evidence of any of the following, as assessed by sponsor approved laboratory, with a single repeat, permitted to assess eligibility, if needed:

- Hepatitis B virus, defined by presence of HBsAg;

**NOTE:** while *not* part of the tests assessed in this study, a previously positive hepatitis B surface antibody result due to vaccination is permissible.

- Hepatitis C infection, defined by presence of HCVAb **and** HCV RNA.

2. History of alcohol abuse or binge drinking and/or any other illicit drug use or dependence within 6 months of screening. Binge drinking is defined as a pattern of 5 (male) and 4 (female) or more alcoholic drinks in about 2 hours. As a general rule, alcohol intake should not exceed 14 units per week (1 unit = 8 ounces (240 mL) beer, 1 ounce (30 mL) of 40% spirit or 3 ounces (90 mL) of wine).
3. Screening ***supine*** 12-lead ECG demonstrating QTcF interval >450 ms or a QRS interval >120 ms. If QTcF exceeds 450 ms, or QRS exceeds 120 ms, the ECG should be repeated 2 more times and the average of the 3 QTcF or QRS values should be used to determine the participant's eligibility.
4. Screening ***seated*** SBP  $\geq$ 140 mm Hg or DBP  $\geq$ 90 mm Hg, following  $\geq$ 5 minutes of seated rest. If SBP is  $\geq$ 140 mm Hg or DBP  $\geq$ 90 mm Hg, the BP assessment should be repeated 2 more times and the average of the 3 BP values should be used to determine eligibility.
5. Use of ***chronic*** prescription medications within 7 days or 5 half-lives (whichever is longer) prior to Day 1, or for prohibited medications, use within the required washout/restriction period provided in [Appendix 9](#) and [Appendix 10](#).

**NOTE:** Use of selected, limited prescription and non-prescription medications may be permitted ***on a case-by-case basis*** after approval from the sponsor (refer to [Section 6.9](#) for details).

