#### **5.2.3. *Additional* Exclusion Criteria for Groups 2, 3 & 4 Only (Hepatic Impairment)**

1. Hepatic carcinoma ***or*** hepatorenal syndrome ***or*** limited predicted life expectancy (defined as <1 year in Groups 2 & 3 and <6 months for Group 4 only).
2. A diagnosis of hepatic dysfunction secondary to any acute ongoing hepatocellular process that is documented by medical history, PE, liver biopsy, hepatic ultrasound, CT scan, or MRI.
3. History of surgery that would be expected to alter absorption, distribution, metabolism, or excretion properties of PF-07081532 (eg, status post porta-caval shunt surgery).

**NOTE:** Participants with a transjugular intrahepatic portosystemic shunt are permitted provided that they meet the Child-Pugh criteria.

4. History of gastrointestinal hemorrhage due to esophageal varices or peptic ulcers less than **4 weeks** prior to the screening visit.
5. Signs of clinically active Grade 3 or 4 hepatic encephalopathy (ie, > Grade 2 Portal Systemic Encephalopathy score; refer to [Appendix 11](#)).

6. Severe ascites and/or pleural effusion, except for those categorized in Group 4 who may be enrolled provided participant is medically stable, per the investigator's judgment.
7. Previously received a kidney, liver, or heart transplant.
8. Screening ***supine*** 12-lead ECG demonstrating a QTcF interval >470 ms or a QRS interval >120 ms. If QTcF exceeds 470 ms, or QRS exceeds 120 ms, the ECG should be repeated 2 more times and the average of the 3 QTcF or QRS values should be used to determine eligibility.
9. At screening, Day -1 or pre-dose on Day 1, persistent severe, uncontrolled hypertension as outlined below:
  - **Groups 2, 3 and 4 at screening or Day -1: *seated*** SBP  $\geq$ 180 mm Hg or DBP  $\geq$ 105 mm Hg after  $\geq$ 5-minute of seated rest, with a single repeat permitted to assess eligibility, if needed, at each of these 2 visits; if done, the repeat assessment overrides initial results.
- NOTE: For participants with SBP  $\geq$ 160 and  $\leq$ 179 mm Hg **or** DBP  $\geq$ 100 and  $\leq$ 104 mm Hg at screening, the period between screening and Day -1 may be used to refine the doses of the agents used for management of BP with the aim of having stable BP by Day -1.

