## 10.8. Appendix 8: ECG Findings of Potential Clinical Concern

ECG Findings That May Qualify as AEs

Marked sinus bradycardia (rate <40 bpm) lasting minutes.

New PR interval prolongation >280 ms.

New prolongation of QTcF to >480 ms (absolute) or by <math>\geq</math>60 ms from baseline.

New-onset atrial flutter or fibrillation, with controlled ventricular response rate: ie, rate <120 bpm.

New-onset type I second-degree (Wenckebach) AV block of >30 seconds' duration.

Frequent PVCs, triplets, or short intervals (<30 seconds) of consecutive ventricular complexes.

ECG Findings That May Qualify as SAEs

QTcF prolongation >500 ms.

New ST-T changes suggestive of myocardial ischemia.

New-onset LBBB (QRS complex >120 ms).

New-onset right bundle branch block (QRS complex >120 ms).

Symptomatic bradycardia.

Asystole:

In awake, symptom-free participants in sinus rhythm, with documented periods of asystole <math>\geq</math>3.0 seconds or any escape rate <40 bpm, or with an escape rhythm that is below the AV node.

In awake, symptom-free participants with atrial fibrillation and bradycardia with 1 or more pauses of at least 5 seconds or longer.

Atrial flutter or fibrillation, with rapid ventricular response rate: rapid = rate >120 bpm.

Sustained supraventricular tachycardia (rate >120 bpm) ("sustained" = short duration with relevant symptoms or lasting >1 minute).

[figure not shown]
- Ventricular rhythms >30 seconds' duration, including idioventricular rhythm (HR <40 bpm), accelerated idioventricular rhythm (HR >40 bpm to <100 bpm), and monomorphic/polymorphic ventricular tachycardia (HR >100 bpm [such as torsades de pointes]).
- Type II second-degree (Mobitz II) AV block.
- Complete (third-degree) heart block.

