Appendix 2. Categorical Classes for ECG and Vital Signs of Potential Clinical Concern

Categories for QTcF

Absolute value of QTcF (msec)	>450 and \leq 480	>480 and \leq 500	>500
Increase from baseline in QTcF (msec)	>30 and \leq 60	>60	

Categories for PR and QRS

PR (ms)	max. \geq 300	
PR (ms) increase from baseline	Baseline $>$ 200 and max. \geq 25% increase	Baseline \leq 200 and max. \geq 50% increase
QRS (ms)	max. \geq 140	
QRS (ms) increase from baseline	\geq 50% increase	

Categories for Vital Signs

Systolic BP (mm Hg)	min. $<$ 90	
Systolic BP (mm Hg) change from baseline	max. decrease \geq 30	max. increase \geq 30
Diastolic BP (mm Hg)	min. $<$ 50	
Diastolic BP (mm Hg) change from baseline	max. decrease \geq 20	max. increase \geq 20
Seated pulse rate (bpm)	min. $<$ 40	max. $>$ 120

Measurements that fulfill these criteria are to be listed in the report.

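### The absolute QTcF >450 ms count in SAP Appendix 2 is confounded with group-specific entry limits (450 v 470 ms), and Appendix 2 lacks the pulse-rate change category that SAP 6.2.3 promises

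*SAP*

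**What the plan says.** **QTcF.** SAP 6.2.4 plans categorical ECG summaries by hepatic group: "Maximum absolute values and changes from baseline for QTcF, PR and QRS will also be summarised descriptively by group using categories". Every post-dose ECG counts, planned or unplanned, and flagged values are listed. In SAP Appendix 2, the row that begins "Absolute value of QTcF (msec" has the bands >450 to 480, >480 to 500 and >500 ms, the same for all groups and regardless of baseline. The next row, which begins "Increase from baseline in QTcF (msec", has the bands >30 to 60 and >60 ms. Protocol 9.3.3.1 uses the same absolute cut-points, also without a baseline condition, and labels the first band as mild prolongation.

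The entry limits differ by group. Protocol 5.2.2 excludes a Group 1 candidate whose screening ECG is one "demonstrating QTcF interval >450 ms or a QRS interval >120 ms". Protocol 5.2.3 excludes a Group 2-4 candidate whose screening ECG is one "demonstrating a QTcF interval >470 ms or a QRS interval >120 ms". In both cases a first reading over the limit is repeated twice and the mean of three decides. Baseline for the analysis is the last pre-dose measurement (SAP 3.2).

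**Pulse rate.** SAP 6.2.3 says that "maximum changes from baseline for seated vital signs will also be summarised descriptively by group using categories" defined in Appendix 2. Appendix 2 has change rows for systolic BP (30 mm Hg either way) and diastolic BP (20 mm Hg either way). For pulse rate it has only the absolute limits <40 and >120 bpm. Protocol 2.3.1 lists increased heart rate as a potential risk. Citing labeling for an injectable drug of the class, it gives mean rises of 2 to 3 bpm, "with some participants experiencing greater increases in resting heart rate, up to 10-20 bpm".

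**The concern.** A Group 2-4 participant who qualifies at 465 ms and stays at 465 ms is counted in the first absolute band, although nothing changed after dosing. A Group 1 candidate whose deciding screening value was 465 ms could not have been enrolled. The absolute row therefore compares groups that were selected differently on the variable being counted.

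Safety by hepatic group is the secondary objective, and with about 6 participants per group one person is 1/6 = 17%. A single unchanged participant can make a group look different on a row that the protocol labels as prolongation.

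The pulse-rate gap is a plain mismatch between a sentence in the SAP and the table it points to. A rise from 70 to 90 bpm (+20) falls in no Appendix 2 category, although heart-rate increase is a risk the protocol names.

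**Working it through.** **Plan's own figure.** There is none to reproduce. The documents give no expected QTcF rate and no QTcF distribution.

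**Inputs from the documents.** Entry limit L = 450 ms (Group 1) or 470 ms (Groups 2-4), with the mean-of-three repeat rule; counting threshold 450 ms; about 6 participants in Group 1 and 18 in Groups 2-4.

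**Assumptions not in the documents.** True QTcF T is normal with mean μ and between-subject SD 18 ms. Each ECG adds independent within-person error with SD 6 or 10 ms. There is no drug effect, and μ is the same in all groups, so only L differs.

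**Model.** Screening S = T + error. If S > L, the mean of three readings must be ≤ L. Among those admitted, baseline B = T + error and one post-dose reading Y = T + error. A participant is counted if Y > 450. Rates are from simulation; the last digit moves by about 0.1 point between runs.

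| True mean (ms) | Group 1 v Groups 2-4, within-person SD 6 | Same, within-person SD 10 |
|---|---|---|
| 400 | 0.2% v 0.4% | 0.6% v 0.8% |
| 410 | 0.9% v 1.7% | 1.9% v 2.6% |
| 420 | 2.5% v 5.5% | 4.6% v 7.0% |
| 430 | 5.6% v 13.6% | 9.3% v 15.5% |
| 440 | 10.1% v 26.8% | 15.9% v 28.3% |

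At 415 ms and SD 6 the rates are about 1.5% v 3.2%.

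**Extra participants expected from the higher limit alone (SD 6).** This is 18 × (rate at limit 470 − rate at limit 450):
- 415 ms: 18 × (0.032 − 0.015) = 0.3
- 430 ms: 18 × (0.136 − 0.056) = 1.4
- 440 ms: 18 × (0.268 − 0.101) = 3.0

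**Chance that the observed pooled hepatic percentage exceeds that of Group 1 (SD 6, binomial, 18 v 6).** 7% at 400 ms, 25% at 410, 55% at 420, 71% at 430 and 81% at 440.

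**Where the gap comes from (430 ms, SD 6).** Participants newly above 450 ms (B ≤ 450, Y > 450) are 3.2% v 4.1%. Those already above it at baseline are 5.6 − 3.2 = 2.4% v 13.6 − 4.1 = 9.5%. So 7.1 of the 8.0 points of difference are people who were above 450 ms before dosing, which the planned table cannot show.

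**The increase row.** The rate of Y − B > 30 ms is the same in both: 0.02% at SD 6 and 1.7% at SD 10. The entry limits do not affect it.

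**Pulse rate.** No arithmetic is needed: 6.2.3 refers to change categories for seated vital signs, and Appendix 2 supplies them for systolic and diastolic BP only.

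**The case against.** The strongest reply is that the plan already separates baseline from drug effect. The same sentence and the same table give increase-from-baseline categories, continuous QTcF changes are summarised by group, and flagged values are listed. A participant at 465 ms before and after dosing appears in the absolute row and in no increase row. This stands as partial mitigation. It does not tell the reader of the table how many of those above 450 ms started there.

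Several further limits stand in full.
- A reader might infer that the table will show a hepatic excess, perhaps several of 18 participants. The documents do not support that, because large counts need an assumed longer QTcF in hepatic impairment. With true means of 410 v 430 ms (SD 6) the rates are 0.9% v 13.6%. But the hepatic rate would be 5.6% even with a 450 ms limit, so 5.6 − 0.9 = 4.7 of the 12.7 points come from the assumed means.
- Group 1 is capped only at screening and can exceed 450 ms later by ordinary variation.
- The output is descriptive; SAP 5.1 rules out tests and decision rules.
- A reader might see an inconsistency with the PR rows or with protocol Appendix 8. Only the PR increase row depends on baseline; the absolute PR and QRS rows do not. Appendix 8, with its "New prolongation of QTcF to" above 480 ms, lists findings that may be adverse events and is not a tabulation rule.
- A reader might infer that pulse rises go unseen. They do not: continuous changes in pulse rate (SAP 6.2.3) and in ECG heart rate (SAP 6.2.4) are summarised by group. The 10-20 bpm figure describes some participants in labeling for another drug, not the expected effect here.

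**Conclusion.** The point holds in a limited form. The absolute QTcF >450 ms row is confounded with the entry limits and can show a hepatic-group excess without a drug effect. The direction was the same in every scenario run. The size is not known: from the limits alone it runs from negligible at a true mean of 400 ms to about 3 extra participants of 18 at 440 ms (SD 6). All of this rests on assumed normal QTcF distributions, one post-dose ECG per person and the stated SDs.

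The risk is that a descriptive table is misread; no wrong inference is built into the plan. The pulse-rate mismatch needs no assumption, but only the categorical count is missing. Both are worth correcting because the cost is very small, and neither threatens the study's primary objective.

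**What to change.** - **SAP 6.2.4 and Appendix 2, QTcF.** Keep the absolute and increase rows. Present the absolute categories as baseline category (≤450, >450 to 480, >480 to 500, >500 ms) by maximum post-dose category within each group, or flag which counts are new. Align protocol 9.3.3.1 by reference if it is amended for another reason.
- **Do not replace the absolute count with a new-only count.** A move from 452 to 479 ms is +27 ms. It stays within one absolute band and below the >30 ms row, so a new-only rule would remove it from every categorical row. A new-only count would also still differ between groups if true means differ (0.6% v 4.1% at 410 v 430 ms, SD 6).
- **SAP Appendix 2, pulse rate.** Add an increase-from-baseline row beside the BP change rows, with a reporting cut-off that the sponsor prespecifies, for example one drawn from the 10-20 bpm range in protocol 2.3.1.

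The cost is SAP wording and table shells. The pre-dose and post-dose data are already collected. The one drawback is sparse cells in a shift table at about 6 per group.
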